10.1 Protection of Human Subjects

10.1.1 Compliance with Informed Consent Regulations (US 21 CFR Part 50) and Relevant Country Regulations

Written informed consent is to be obtained from each patient prior to enrollment into the study, and/or from the patient's legally authorized representative. If the patient is under the legal age of consent, the consent form must be signed by the legally authorized representative in accordance with the relevant country and local regulatory requirements.

Written parental/legally authorized representative informed consent in addition to a separate written minor consent and/or assent (in accordance with any applicable state and local laws/regulations) are required for each minor study patient prior to study enrollment or any study-related procedures in the study.

10.1.2 Compliance With IRB or IEC Regulations

This study is to be conducted in accordance with IRB regulations (US 21 CFR Part 56.103) or applicable IEC regulations. The investigator must obtain approval from a properly constituted IRB/IEC prior to initiating the study and re-approval or review at least annually. Allergan is to be notified immediately if the responsible IRB/IEC has been disqualified or if proceedings leading to disqualification have begun. Copies of all IRB/IEC correspondence with the investigator should be provided to Allergan.

10.1.3 Compliance With Good Clinical Practice

This protocol is to be conducted in accordance with the applicable GCP regulations and guidelines.

10.1.4 Compliance With Electronic Records; Electronic Signatures Regulations (US 21 CFR Part 11)

This study is to be conducted in compliance with the regulations on electronic records and electronic signature.

10.2 Changes to the Protocol

The investigator must not implement any deviation from or changes of the protocol without approval by Allergan and prior review and documented approval/favorable opinion from the IRB/IEC of a protocol amendment, except where necessary to eliminate immediate hazards to study patients, or when the changes involve only logistical or administrative aspects of the study (eg, change in monitors, change of telephone numbers).

10.3 Patient Confidentiality

A report of the results of this study may be published or sent to the appropriate health authorities in any country in which the study drug may ultimately be marketed, but the patient's name will not be disclosed in these documents. The patient's name may be disclosed to the Sponsor of the study, Allergan, or the governing health authorities or the FDA if they inspect the study records. Appropriate precautions will be taken to maintain confidentiality of medical records and personal information.

10.3.1 Patient Privacy

Written authorization (US sites only), data protection consent (European sites only), and other documentation in accordance with the relevant country and local privacy requirements (where applicable) is to be obtained from each patient prior to enrollment into the study, and/or from the patient's legally authorized representative in accordance with the applicable privacy requirements (eg, the Health Insurance Portability and Accountability Act Standards for Privacy of Individually Identifiable Health Information ("HIPAA"), European Union Data Protection Directive 95/46/EC ["EU Directive"]).

In accordance with HIPAA requirements, additional purposes of this study include the following:

- to publish anonymous patient data from the study; and
- to create and maintain a data repository

10.4 Documentation

10.4.1 Source Documents

Source documents may include a patient's medical records, hospital charts, clinic charts, the investigator's patient study files, as well as the results of diagnostic tests such as X-rays, laboratory tests, and electrocardiograms. The investigator's copy of the case report forms serves as part of the investigator's record of a patient's study-related data.

The following information should be entered into the patient's medical record:

- Patient's name
- Patient's contact information
- The date that the patient entered the study, patient number, and medication kit number
- The study title and/or the protocol number of the study and the name of Allergan
- A statement that informed consent and/or assent, if applicable was obtained (including the date). A statement that written authorization (US sites only), data protection consent (EU sites only), or other country and local subject patient privacy required documentation for this study has been obtained (including the date).
- A statement that patient meets all the inclusion criteria and does not meet any of the exclusion criteria. If a patient does not qualify for the study, a screen failure reason should be noted.
- Dates of all patient visits
- Medical and surgical history
- Documentation of results of all procedures conducted during the course of the trial, including the dose determination process and reason(s) why patient did not meet retreatment criteria. [REDACTED]
- For sites performing the Edinburgh Visual Gait score, the videotape [REDACTED]

- The results of laboratory tests performed by the site (eg, results of hematology, serum chemistry, HbA1c, urine pregnancy, and immunogenicity tests)
- All concurrent medications (list all prescription, non-prescription and herbal medications being taken 3 months prior to or at the time of enrollment). At each subsequent visit, changes to the list of medications and concurrent procedures should be recorded.
- Occurrence and status of any adverse events
- The date the patient exited the study, and a notation as to whether the patient completed the study or reason for discontinuation

10.4.2 Case Report Form Completion

The investigator is responsible for ensuring that data are properly recorded in each patient's eCRF and related documents. An investigator who has signed the protocol signature page should personally sign for the eCRFs (as indicated in the eCRFs) to ensure that the observations and findings are recorded in the eCRFs correctly and completely. The eCRFs are to be completed in a timely manner.

10.4.3 Study Summary

An investigator's summary will be provided to Allergan within a short time after the completion of the study, or as designated by Allergan. A summary is also to be provided to the responsible IRB/IEC.

10.4.4 Retention of Documentation

All study-related correspondence, patient records, consent forms, patient privacy documentation, records of the distribution and use of all investigational products, and electronic copies of eCRFs must be maintained on file.

For countries falling within the scope of the ICH guidelines, the Allergan-specific essential documents should be retained until at least 2 years after the last approval of a marketing application in an ICH region and until there are no pending or contemplated marketing applications in an ICH region or at least 2 years have elapsed since the formal discontinuation of clinical development of the investigational product. These documents should be retained for a longer period, however, if required by the applicable regulatory requirement(s) or if needed by Allergan.

In addition, for countries not falling within the scope of the ICH guidelines, local regulatory requirements should be followed regarding the retention of clinical study documentation.

Allergan requires that it be notified in writing if the investigator wishes to relinquish ownership of the data so that mutually agreed-upon arrangements can be made for transfer of ownership to a suitably qualified, responsible person.

10.5 Labeling, Packaging, and Return or Disposal of Study Medications/Treatments

10.5.2 Clinical Supply Inventory

The investigator must keep an accurate accounting of the number of investigational units received from Allergan, dispensed to the patients, and the number of units returned to Allergan or Allergan designee during and at the completion of the study. A detailed inventory must be completed for the study medication. The study medication must be reconstituted and administered only by appropriately qualified persons to patients in the study. The medication is to be used in accordance with the protocol under the direct supervision of an investigator.

10.5.3 Return or Disposal of Study Medications/Treatments and/or Supplies

All clinical study medications/treatments and/or supplies will be returned to Allergan or Allergan designee for destruction.

10.6 Monitoring by the Sponsor

A representative of Allergan will monitor the study on a periodic basis. The determination of the extent and nature of monitoring will be based on considerations such as the objective, purpose, design, complexity, blinding, size, and endpoints of the study.

Authorized representatives of Allergan or regulatory authority representatives will conduct on-site visits to review, audit and copy study-related documents. These representatives will

meet with the investigator(s) and appropriate staff at mutually convenient times to discuss study-related data and questions.

10.7 Handling of Biological Specimens

Laboratory specimens for blood chemistry panel, hematology and HbA1c, will be sent to a centralized clinical laboratory with certification from a recognized accreditation agency (eg, College of American Pathology [CAP] or Clinical Laboratory Improvement Amendments [CLIA] certification) to be assayed using validated methods. Samples for immunogenicity will be sent to the central laboratory for temporary storage and will then be sent to a specialty laboratory for analysis. Allergan shall have full ownership rights to any biological specimens/samples derived from the study. Approximately 14 mL of blood is estimated to be collected at a given visit for children 15 kg and above (7 mL for hematology and chemistry and 7 mL for immunogenicity testing). Approximately 7 mL of blood will be collected at a given visit for children under 15 kg in weight. Please refer to the Laboratory Manual for details regarding specimen sample collection, processing, storage, and shipping procedures.

10.8 Publications

Allergan as the sponsor, has proprietary interest in this study. Authorship and manuscript composition will reflect joint cooperation between multiple investigators and sites and Allergan personnel. Authorship will be established prior to the writing of the manuscript. As this study involves multiple centers, no individual publications will be allowed prior to completion of the final report of the multicenter study except as agreed with Allergan.

Emissions reduction	75
Green economy	72
Carbon tax	40

A series of five horizontal black bars of varying lengths, decreasing from top to bottom. The bars are evenly spaced and extend across the width of the page.

BOTOX® (Botulinum Toxin Type A) Purified Neurotoxin Complex

[REDACTED]

[REDACTED]

11. **What is the primary purpose of the *Journal of Clinical Oncology*?**

11. **What is the primary purpose of the following statement?**

A solid black horizontal bar, likely a placeholder or a redacted section of the document.

11. **What is the primary purpose of the *Journal of Clinical Oncology*?**

12.2 Package Insert/Summary of Product Characteristics

The appropriate package insert or Summary of Product Characteristics will be supplied to investigators in countries where the product is marketed.

12.3 Glossary of Abbreviations

Term/Abbreviation	Definition
AFO	ankle foot orthosis [REDACTED]
BoNT-A	botulinum neurotoxin type A
BOTOX®	Botulinum Toxin Type A Purified Neurotoxin Complex (US adopted name onabotulinumtoxinA), referred to as BOTOX
CFR	Code of Federal Regulations (US) [REDACTED]
CNS	central nervous system [REDACTED]
D	day
ECG	electrocardiogram
eCRF	electronic case report form
EDC	electronic data capture
ELISA	enzyme-linked immunosorbent assay
EMG	electromyography
EU	European Union
GCP	Good Clinical Practices [REDACTED] [REDACTED]
HbA1c	glycosylated hemoglobin
HIPAA	Health Insurance Portability and Accountability Act Standards for Privacy of Individually Identifiable Health Information
ICH	International Conference on Harmonisation
IEC	Independent Ethics Committee
IRB	Institutional Review Board
ITT	intent-to-treat
IVRS	interactive voice response system
IWRS	interactive web response system [REDACTED] [REDACTED]
NA	not applicable
No.	number

NOAEL	No-observable-adverse-effect level
OT	occupational therapy
PT	physical therapy
Scrn	screening
SDRC	Safety Data Review Committee
Tx	treatment
U	unit, corresponding to the median lethal dose (LD ₅₀) in mice
US	United States
V1	slow velocity
V3	fast velocity
Wk	week

12.4 Protocol Amendment 1 Summary

Title: BOTOX® Treatment in Pediatric Lower Limb Spasticity: Open-label Study

Protocol 191622-112, Amendment 1

Date of Amendment: 30 March 2012

Amendment Summary

This summary includes changes made to Protocol 191622-112 (02 December 2011) to provide clarifications, updated information, and corrections.

Following is a summary of content-oriented changes that were made to each section of the protocol, and a brief rationale for these changes. Minor editorial and document formatting revisions have not been summarized.

Section(s)	Revision	Rationale
Title page	Added EudraCT number and changed Allergan Medical Safety Physician.	Updated information.
10.7, Handling of Biological Specimens	Revised approximate volume of blood collection for hematology and chemistry regardless of weight from 5 to 7 mL and total for children 15 kg and above from 12 to 14 mL.	Based on the revised central laboratory (Covance) requirements.

Section(s)	Revision	Rationale
[REDACTED]	[REDACTED]	[REDACTED]
[REDACTED]	[REDACTED]	[REDACTED]

12.5 Protocol Amendment 2 Summary

Title: BOTOX® Treatment in Pediatric Lower Limb Spasticity: Open-label Study

Protocol 191622-112, Amendment 2

Date of Amendment: 29 November 2012

Amendment Summary

This summary includes changes made to Protocol 191622-112 Amendment 1 (e-signature date 02 April 2012) to provide clarifications and corrections.

Following is a summary of content-oriented changes that were made to each section of the protocol, and a brief rationale for these changes. Underlining is used to identify wording that has been added and strikethrough for wording that has been deleted. Minor editorial and document formatting revisions have not been summarized.

Section(s)	Revision	Rationale
Summary	Changes corresponding to those identified below in the body were made to the Summary section.	For consistency within the protocol
Tables 1 and 2, Schedules	[REDACTED]	[REDACTED]
1.4, Dose Justification 2.2, Clinical Hypothesis 5.4, Treatment Regimen and Dosing Table 3	Added wording for a combination of both lower limbs for diplegic patients	Allows a dose up to 10 U/kg and not to exceed 340 U to be injected during treatment cycles 2 to 5 when both lower limbs are treated

Section(s)	Revision	Rationale
1.4, Dose Justification	Second paragraph: The maximum lower limb dose in a single limb doses selected for in this study corresponds to the maximum high dose group (8 U/kg) from the efficacy Study 191622-111. This dose is These doses are supported by Allergan clinical trial experience in pediatric lower limb spasticity, clinical expert advice, published literature including consensus guidelines for botulinum toxin type A treatment of pediatric spasticity, and nonclinical toxicology data.	For clarification
3, Study Design	Replaced details regarding dosing with a cross reference to Section 5.4, Treatment Regimen and Dosing	To consolidate dosing information in a clearly designated section
4.4, Exclusion Criteria	Changed #23 regarding history of fracture in the study upper limb within 12 months from “prior to the screening visit” to “prior to the day 1 visit.”	For consistency with other criteria
4.5.2, Prohibited Medications/Treatments	Added to the wording that requires a patient to remain on a stable dose of anti-spastic medications: to the extent possible unless judged by the investigator to be clinically inappropriate.	For clarification
5.3, Method for Assignment to Treatment Groups	Added At the study day 1 visit for both de novo and rollover, the site will access the IVRS/IWRS to enroll the patient;	For clarification

Section(s)	Revision	Rationale
5.4, Treatment Regimen and Dosing	At the beginning of 5.4, replaced similar wording that was in 5.4.2 and 5.4.3 with: If a patient meets the retreatment criteria, including no indication of an unacceptable safety risk, and it is considered to be clinically appropriate by the investigator, the patient should receive at least 4 U/kg in the study lower limb(s) every 12 to 14 weeks, with the total dose not to exceed the maximum specified for each treatment cycle.	For clarification
5.4.1, Treatment Cycle 1 for De Novo Patients	Specified that a total of 8 U/kg is to be injected either in the single study lower limb or divided between both study lower limbs only for diplegic patients.	For clarification
5.4.3, Treatment Cycles 2 Through 5 for All Patients (Rollover and de novo)	Revised description of dose limitations	For clarification
Table 3	Revised title to be more specific (Maximum Per-muscle, Per-limb, and Total Body Dose), added row for total maximum dose for both lower limbs, and added footnote to indicate that only 1 upper limb is to be injected.	For clarification
5.4.4, Treatment Regimen/Dosage Adjustment	Added For purposes of dose calculation, the patient's weight will be rounded to the nearest whole kilogram.	For clarification
5.4.4.1, Retreatment Criteria	Revised to “Patients should may be re injected” if they meet the retreatment criteria.	For clarification

Section(s)	Revision	Rationale
8.7, Early Discontinuation of Patients	Revised study week 42 to study week 48.	Correction
8.8, Withdrawal Criteria	Added that patients will be withdrawn from the study if they develop a medically significant hypersensitivity reaction to the study drug such as angioedema or anaphylaxis, or if a patient becomes pregnant during the study.	For clarification

Section(s)	Revision	Rationale
[REDACTED]	[REDACTED]	[REDACTED]
[REDACTED]	[REDACTED]	[REDACTED]
[REDACTED]	[REDACTED]	[REDACTED]

12.6 Protocol Amendment 3 Summary

Title: BOTOX® Treatment in Pediatric Lower Limb Spasticity: Open-label Study

Protocol 191622-112, Amendment 3

Date of Amendment: January 2014

Amendment Summary

This summary includes changes made to Protocol 191622-112 Amendment 2 (e-signature date 28 November 2012). [REDACTED]

[REDACTED]

[REDACTED]

Following is a summary of content-oriented changes that were made to each section of the protocol, and a brief rationale for these changes. Minor editorial and document formatting revisions have not been summarized.

Section(s)	Revision	Rationale
Title page	Referred to the Study Contacts Page for emergency telephone numbers; updated page 2	Per new Allergan protocol template
3.1	Changed “members” to “participants” and removed “or investigator” from the examples given of ad hoc SDRC participants	Clarification
Protocol Summary; 4.4	Modified Exclusion Criterion 13a regarding seizure frequency for exclusion Modified Exclusion Criterion 14 regarding vulnerable respiratory state Added Exclusion Criterion 29 to exclude patients with significant suicidality from treatment	Clarification Clarification To avoid confounding the safety data

Section(s)	Revision	Rationale
Protocol Summary;	[REDACTED]	[REDACTED]
	[REDACTED]	[REDACTED]
	Added a sentence on use of anti-epileptics	Clarification that anti-epileptics are permissible during the study
5.4.1.1	Amended bullet (c) of the retreatment criteria	To specify that patients who experience certain adverse events will not receive further study treatments
5.4.5	Revised paragraph regarding retreatment for patients with adverse events of compromised respiratory function, aspiration, difficulty swallowing, or clinically significant excessive salivation	To specify that patients who experience these adverse events will not receive further study treatments
6.4	Removed: “Non-frost-free -20°C freezer for storage of serum neutralizing antibody samples” Added bullet that Allergan will supply a kilogram-only weight scale for selected sites, and that the site will supply it only if it is not already supplied by Allergan	Correction To ensure that patient's weight is collected in kilograms only
	[REDACTED]	[REDACTED]
9.3	Updated serious adverse event language	Per new Allergan protocol template
	[REDACTED]	[REDACTED]

ALLERGAN

Protocol 191622-112 Amd 3

There will be up to 5 treatments in the study. For the first treatment cycle, de novo patients (who did not participate in Allergan Study 191622-111) are to receive a total of 8 U/kg (not to exceed 300 U) either in a single affected lower limb or divided between both study limbs (referred to as the study lower limb(s)).

Rollover patients (who participated in Allergan Study 191622-111) during the first treatment cycle may receive up to a maximum of 8 U/kg (not to exceed 300 U) in the same lower limb that was treated in Study 191622-111 (referred to as the study lower limb). Patients with clinically significant upper limb spasticity may be eligible to receive BOTOX treatment in an affected upper limb up to a maximum of 8 U/kg (not to exceed 300 U). The combined lower and upper limb dose should not exceed 8 U/kg or 300 U, whichever is lower, during the first cycle.

For treatment cycles 2 through 5, the maximum dose for a single lower limb or a single upper limb remains the same as for treatment cycle 1; the maximum dose for combined upper and lower limbs or for both lower limbs only for diplegic patients can be increased to 10 U/kg (not to exceed 340 U).

If a patient meets the retreatment criteria, including no indication of an unacceptable safety risk, and it is considered clinically appropriate by the investigator, the patient should receive at least 4 U/kg in the study lower limb(s) every 12 to 14 weeks, with the total dose not to exceed the maximum specified for each treatment cycle.

Approximately 350 patients will be enrolled. The sample size was determined empirically rather than by sample size calculation.

[figure not shown]
1.2 Secondary and Other Objectives

[figure not shown]
There are no secondary or other objectives for this study.

2. Analysis Populations and Data Conventions

2.1 Analysis Populations

Safety data will be analyzed on the basis of all treated patients based on the treatment received, defined as the safety population.

2.3 Data Conventions

The data conventions and definitions listed in this section are to be applied to all analyses unless stated otherwise in a subsequent section of this Analysis Plan.

- Data will be analyzed according to the following treatment groups:
 - For rollover patients from Study 191622-111 under treatment group BTX 4 U/kg, BTX 8 U/kg, or Placebo, their corresponding treatment group will be

designated as BTX 4 U/kg/BTX, BTX 8 U/kg/BTX, Placebo/BTX, respectively.

- For de novo patients, , their treatment group will be designated as Placebo/BTX.
- Concurrent medication and prior medication will be calculated using the following convention: 1) If the stop date of taking medication is prior to first injection date, then it will be counted as prior medication; 2) If the start date of taking medication is after or on first injection date, then it will be counted as concomitant medication; 3) If the start date of taking medication is prior to first injection date and stop date is on or after last injection date, then it will be counted as both prior medication and concomitant medication.
- Concurrent procedures are defined as those taken on or after the first injection date.
- All data will be listed with the exceptions of commonly expected results such as physical examination, pregnancy tests results for females when not applicable, etc.
- Summary statistics of continuous variables will include the sample size (N), mean, standard deviation, median, minimum (Min), and maximum (Max).
- Summary statistics of categorical variables will include the sample size (N) and/or frequency counts and percentages.
- Medical Dictionary for Regulatory Activities (MedDRA) nomenclature will be used to code all adverse events (AEs) and medical history.
- World Health Organization Drug Dictionary Enhanced (WHO DDE) preferred name and MedDRA will be used to code all medications.
- Metric systems will be used for all applicable measures including (kg), height (cm), and clinical laboratory data (SI: Standard International units).
- Baseline is defined as the last non-missing observation prior to receiving the first treatment for de novo patients and the same baseline in study 191622-111 for the rollover patients. For some measurements not measured in study 191622-111, the last non-missing observation prior to receiving the first treatment in study 191622-112 will be used. Change from baseline is calculated as follow-up minus baseline value.

- Missing values will not be imputed.
- Study days from the treatment day of a certain treatment cycle will be calculated as:

Study days = visit date – most recent treatment day visit date + 1.

- The study day of an event that has occurred before first treatment day will be calculated as:

Study day = date of event – treatment 1 visit date.

- Partial dates occurring when calculation of study day is germane to the study outcome will be handled as follows:

If the year is missing then the date is treated as missing.

If either the month or the day is missing, then the closest to baseline possible will be used. That is, an event occurring the year before baseline would use December and/or the last day of the month. An event occurring the year after baseline would use January and/or the first day of the month.

All partial dates will be listed “as is” in the data listings.

- All adverse events (AEs) with missing onset dates will be identified and the missing dates will be imputed as follows for analysis. These imputations are only for assigning adverse events to a particular study phase; calculations such as days to onset will not use these imputations. All partial dates will be listed “as is” in the data listings.
 - (a) For AE onset date: If day and month are missing but year is available (..../yy) then the imputed day and month will be 01/01/yy or the injection date if they have the same year, whichever is later. If day is missing but the month and year are available (mm..../yy), then the imputed day will be mm/01/yy or the injection date if they have the same month and year, whichever is later.
 - (b) For AE stop date: If day and month are missing but year is available (./.yy) then the imputed day and month will be 12/31/yy or the study exit date if they have the same year, whichever is earlier. If day is missing but the month and year are available (mm./.yy), then the imputed day will be the last day of the month mm in the year yy or the study exit date if they have the same month and year, whichever is earlier.

- (c) If the AE onset or stop month, day, and year are missing (..../..), then the study entry date will be used as the AE onset date and the exit date will be used as the AE stop date.
- Data from unscheduled visits or re-test visits will be treated the same way as scheduled visits, i.e., the dates of such visits will be used in the categorization of visit window. The algorithm handling multiple visits within a visit window will also be applied to unscheduled visits and re-test visits.
- There is no data pooling for efficacy analyses considering all are descriptive evaluations.
- The mean change from baseline for a given treatment group will be calculated by taking the sum of all individual changes from baseline divided by the number of patients with observations in that treatment group. As a consequence, patients without the particular follow-up data will not be taken into account, except if there is a missing value replacement method used.

3. Disposition and Exit Status

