6.2 Treatment Emergent Adverse Events

Adverse events are collected for the period prior to the first treatment (which are referred to as pre-treatment AEs as cited in Section [Error! Reference source not found.](#)) and for the period on or after the first treatment.

An overall treatment-emergent adverse event (TEAE) is an adverse event with onset on or after the initiation of the first treatment or an adverse event with onset prior to the first treatment that worsened in severity or became serious on or after the initiation of the first treatment.

A treatment cycle treatment-emergent adverse event (TEAE) is an adverse event with onset on or after the initiation of the cycle treatment but before the initiation of the next cycle treatment or an adverse event with onset prior to the cycle treatment that worsened in severity or became serious on or after the initiation of the cycle treatment but before the initiation of the next cycle treatment.

An AE that stops during certain treatment cycle and recurs in the subsequent treatment cycle(s) is considered as a TEAE in the subsequent treatment cycle(s) if it fulfills the TEAE definition above.

The number and percentage of patients reporting each event will be summarized by treatment cycle and overall as follows:

- i. By primary SOC and preferred term. At each level of summarization (overall, primary SOC, and preferred term) a patient will be counted once if he/she reports 1 or more experiences at that level.
- ii. By primary SOC, preferred term and severity. For a given adverse event of a patient, if more than 1 severity grade was reported, the worst severity grade will be included in the tabulation.

An overall summary of TEAE will be presented. In addition, individual patient data listings (including adverse event listings that include the investigator verbatim terms and MedDRA lower level terms) will be provided.

Furthermore, the assessment of possible distant spread of toxin will be performed using the list of 39 MedDRA preferred terms (version 19.0 or its updated version as appropriate during the time of data analysis).

MedDRA Preferred Terms Evaluated for Possible Distant Spread of Toxin

Cardiac Disorders

Bradycardia

Eye Disorders

Accommodation disorder
Diplopia
Extraocular muscles paresis
Eyelid function disorder
Eyelid ptosis
Pupillary reflex impaired
Vision blurred

Gastrointestinal Disorders

Constipation
Dry mouth
Dysphagia
Ileus paralytic

Infections and Infestations

Botulism

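### SAP 2.3 rule (a) can impute an adverse event onset after the event had ended, so an event that was over before the first injection is counted as a TEAE.

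*SAP*

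**What the plan says.** SAP 2.3 (Data Conventions) has three rules for incomplete adverse event dates. Their purpose is narrow: "These imputations are only for assigning adverse events to a particular study phase".

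- Rule (a), day of onset missing: "then the imputed day will be mm/01/yy or the injection date if they have the same month and year, whichever is later". Day and month missing: "then the imputed day and month will be 01/01/yy or the injection date if they have the same year, whichever is later".
- Rule (b), day of stop missing: "then the imputed day will be the last day of the month mm in the year yy or the study exit date", whichever comes first. Nothing ties the stop date to the onset or to an injection.
- Rule (c), date wholly missing: "then the study entry date will be used as the AE onset date".

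SAP 6.2 then sorts events by onset, or by later worsening. Overall: "An overall treatment-emergent adverse event (TEAE) is an adverse event with onset on or after the initiation of the first treatment". By cycle: "A treatment cycle treatment-emergent adverse event (TEAE) is an adverse event with onset on or after the initiation of the cycle treatment" and before the next one. The tables follow both definitions: "The number and percentage of patients reporting each event will be summarized by treatment cycle and overall as follows". The same section says that events before the first treatment are also collected. SAP 1.1 allows up to five treatments.

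**The concern.** Rule (a) never asks whether the event was already over on the injection date. When a recorded stop date precedes that injection, the rule gives an onset later than the stop, and SAP 6.2 counts the event as emergent from an injection that had not yet been given.

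The sequence needed is an ordinary one. Protocol 9.1.1 has adverse events queried at the start of every visit. Protocol 5.4.4.1 has retreatment eligibility checked before the injection on the same day, and lets a patient be reconsidered once an event or muscle weakness has resolved. Muscular weakness is also one of the distant-spread terms in SAP 6.2.

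Adverse event incidence, overall and by cycle, is the main safety output of a study whose only objective is long-term safety. A misplaced event either adds a treatment-emergent event that did not occur on treatment, or takes an event from one cycle and gives it to the next. The second blurs comparison across repeated doses.

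Rule (a) also refers to a single injection date without saying which of up to five it means.

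**Working it through.** **Logic on constructed dates.** The plan gives no figure to reproduce, so I applied rule (a) as written to injections 12 weeks apart: 20 January, 14 April, 7 July, 29 September and 22 December of a non-leap year.

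1. *Before the first injection.* Onset in January (day unknown), stop 10 January. The later of 1 January and 20 January is 20 January, ten days after the event ended, so it becomes a cycle 1 TEAE. The result is the same whether the rule means the first injection, the earliest match or the latest match.
2. *Before a reinjection.* Onset in April (day unknown), stop 8 April. If reinjections count, the imputed onset is 14 April, six days after the stop, and the event moves to cycle 2. If only the first injection counts, the onset becomes 1 April and the event correctly stays in cycle 1.
3. *The reverse error.* If only the first injection counts, a month-only event that truly began on 20 April is imputed to 1 April. It goes to cycle 1 instead of cycle 2.
4. *Year-only onset.* With the latest match, both events above go to 22 December, cycle 5. With the earliest match, both go to 20 January: wrong for the first, right for the second.

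**How often the imputed onset falls after the stop (month-only, reinjections included).** Assumptions: five treatments 84 days apart, so four reinjections and 420 days to exit (last treatment at week 48, exit 12 weeks later, Protocol 3); every calendar start date equally likely; onset uniform over follow-up; stop date complete.

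Let the event last *d* days and the reinjection fall on day *D* of its month. The stop precedes the injection for max(0, *D* − *d*) onset days. Summed over a month of *L* days this is (*L* − *d*)(*L* − *d* + 1)/2. A year has seven months of 31 days, four of 30 and one of 28:

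| *d* | Sum over the year | Mean per reinjection (÷ 365) | Share = 4 × mean ÷ 420 |
|---|---|---|---|
| 7 | 7×300 + 4×276 + 231 = 3435 | 9.41 | 9.0% |
| 14 | 7×153 + 4×136 + 105 = 1720 | 4.71 | 4.5% |
| 28 | 7×6 + 4×3 + 0 = 54 | 0.148 | 0.1% |

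A day-by-day enumeration gives the same shares. With four treatments 98 days apart (three reinjections, 378 days) they are 3 × 9.41/378 = 7.5%, 3 × 4.71/378 = 3.7% and 0.1%.

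**Sensitivity to timing.** Two dates in one month differ by at most 30 days. With at least 84 days between injections, an event that starts within 53 days of an injection cannot share a month with the next one. If all onsets fall in that span, the share is 0%.

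**What a stop-date check cannot repair.** Not knowing the day puts 4 × 14.72/420 = 14.0% of month-only events in the wrong cycle, whatever their length (14.72 = 5373/365, the mean of day of month minus 1). The check removes the shares in the table and leaves 5.1%, 9.5% and 13.9% for 7-, 14- and 28-day events.

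**Scale of one error.** One patient whose only report of a term is misplaced changes its incidence by 1/350 = 0.29 percentage points, if 350 patients are treated.

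**The case against.** *Placing an unknown onset after treatment is the conservative choice.* This stands when the stop date is missing or falls on or after the injection, and the fix keeps it. It fails when a known stop date rules that onset out. By cycle it is not conservative either, because the earlier cycle loses the event. SAP 2.3 already makes the check for medications: one stopped before the first injection is classed as prior.

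*The next-cycle error depends on how the injection date is read.* This stands. A reader might infer that rule (a) always pushes events to a later cycle. The documents do not support that: if only the first injection is meant, the error runs to the earlier cycle. That reading is weaker, because TEAEs are tabulated by cycle, but SAP 6.2 itself divides collection at the first treatment, and study phase is not defined. Only the error before the first injection holds on every reading.

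*The 14.0% looks like the size of the defect.* It is not. It is the total cost of not knowing the day. Events already over reach that share only if they last one day, and a one-day event with a complete stop date has a known onset day.

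*An unseen rule may override this.* It cannot be excluded. Text before SAP 6.2 is blacked out, the reference there to pre-treatment events is broken, and SAP 2.3 yields to later sections.

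*The consequence is low.* Largely true. The study is open-label with no control, no hypothesis test is planned unless otherwise specified, and partial dates are listed as recorded, so a misplaced event can be traced. The tables would still be wrong.

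**Conclusion.** As written, rule (a) can date an event after its own recorded end, and SAP 6.2 then counts it in the wrong period. The certain part is the event that began and ended before the first injection in the same month or year: it becomes a TEAE on any reading. This concerns mainly de novo patients, because for rollover patients the exit visit of the preceding study serves as day 1. The move into the next cycle is conditional on reinjections being covered. That is the likely intention, but the SAP must say so.

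The size is small and cannot be fixed from the documents, which give no count of partial-date events. The shares of about 9%, 4.5% and 0.1% apply to month-only events with a complete stop date, not to all events. They assume 84-day intervals and uniform onset, and fall towards zero if onsets cluster soon after injection. No share is given for the pre-treatment error, because the length of screening is not visible. This is a point to consider: a clear rule error, cheap to correct, with modest effect on the tables.

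**What to change.** Rule (a), one sentence: *Use the latest injection date in the known month or year that is not after the AE stop date (known, or imputed under (b)); if none qualifies, use the first day of the known month or year.* This also settles which injection applies. In the two examples the onsets become 1 January (pre-treatment) and 1 April (cycle 1).

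Rule (c), one sentence: *An AE with a wholly missing onset and a known stop date before the first injection is pre-treatment.*

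The cost is a small programming change. Overall TEAE incidence may fall slightly, but only for events that had ended before the first injection. Some limits remain and should be stated. Events that span an injection are still assigned to the later cycle. So are events recorded as stopping on the injection day, including those found resolved at the retreatment visit. A year-only onset without an informative stop date goes to the last injection of that year, which is a convention.
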